- b) **Block Quality:** Achieving an inability to sense cold ice-water in the cutaneous distribution of the brachial plexus trunk distal to the block within 30 minutes will be considered a **successful nerve block** preoperatively. If the patient has an inability to sense cold ice-water in the cutaneous distribution of the brachial plexus trunk distal to the block within 30 minutes will be considered a **successful nerve block** postoperatively. Anything less will be considered a **failed nerve block**.

12) Secondary Outcomes:

- i) Return of sensory function in the blocked area of the limb.
- ii) Return of motor function in the blocked area of the limb.
- iii) Post-op Nausea and vomiting before discharge
- iv) Nausea and Vomiting after discharge
- v) Changes in Blood Pressure (BP) in the PACU defined as any blood pressure +/- 20% of patient's baseline (either BP on admission if no clinic BP is documented, or most recent clinic BP as documented if that exists)
- vi) Changes in Blood Pressure in Second Stage defined as any blood pressure +/- 20% of patient's baseline (either BP on admission if no clinic BP is documented, or most recent clinic BP as documented if that exists)

Motor Block Scale Table

Muscle function level	Scale	
	Grade	Percent of normal
No evidence of contractility	0	0 %
Slight contractility, no movement	1	10 %
Full range of motion with gravity eliminated	2	25 %
Full range of motion against gravity	3	50 %
Full range of motion against gravity, some resistance	4	75 %
Full range of motion against	5	100 %

gravity, full resistance		
--------------------------	--	--

Definitions:

- a) Duration of Analgesic Block
 - i) Time from nerve block-needle withdrawal until the **time reported by the patient** that they first had awareness of painful sensation returning anywhere in the surgically operated upon area of the limb.
 - ii) Patient will be given a form to write time down as it occurs.
 - iii) They are expected to write down the date and time (hour and minute) they first perceive pain in the arm anywhere in the surgical area. (even if they wake up from sleep and first notice pain there).
 - iv) They will be telephoned within three days from the block to gather the data from the patient.
 - v) If they cannot find the form or did not write the date and time down, we will then use the date and time the patient recalls from memory.
- a) Duration of Sensory Block

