 - i) Time from nerve block-needle withdrawal until the **time reported by the patient** that they first had awareness of tactile (light touch) sensation returning anywhere in the blocked area. Patients will be given a form to write time down as it occurs. They are expected to write down the date and time (hour and minute) they first felt sensation return to the blocked area (even if they wake up from sleep and first notice sensation returned).
 - ii) They will be telephoned within three days from the block to gather the data from the patient.
 - iii) If they cannot find the form or did not write the date and time down, we will then use the date and time the patient recalls from memory.
- a) Approximate Duration of Motor Block
 - i) Time from nerve block-needle withdrawal until the **time reported by the patient** that, with the arm of the blocked extremity, they are able to **flex their bicep**. Patient will be given a form with a diagram and instruct them prior to sedation and placing the block. They will write the time down when they are able to achieve this outcome. They are to write down the date and time (hour and minute) they were first able to flex their bicep on the blocked limb.
 - ii) They will be telephoned within three days to gather the time from the form.
 - iii) If they cannot find the form or did not write the data down, we will then use the time the patient recalls from memory.
- a) Patient Satisfaction with the block
 - i) Patients will be asked the question: "Would you want a nerve block again if you needed a similar surgery in the future?" Yes / No

Secondary Outcomes Table

Did patient have nausea before discharge	
Yes	No
Did patient have vomiting before discharge	
Yes	No
Did patient have nausea after discharge (72 hours)	
Yes	No
Did patient have vomiting after discharge (72 hours)	
Yes	No
Did the patient have +/- 20% deviation of baseline Blood pressure in PACU from admission	
Yes	No
Did the patient have +/- 20% deviation of baseline Blood pressure in Second Stage Recovery from admission	
Yes	No

2) Study Background Information:

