- d) Patients giving informed consent.

2) Exclusion Criteria:

Patients who have or are:

- a) An inability to cooperate during the block placement.
- b) Any neuropathy
- c) Diabetes
- d) Documented kidney disease
- e) Documented Hepatic disease

- f)** A lack of or inability to give informed consent.
- g)** Currently incarcerated.
- h)** Pregnancy

3) Consent:

- a) The study will be explained to the patient's satisfaction, their questions will be answered, and informed consent will be obtained from the patient after explanation of the risks, benefits, and alternatives.
- b) Once the patient has consented to the study, they will be included in the study and followed throughout.
- c) Patients with failed blocks will be included in the intention to treat analysis.
- d) If the block is unable to be placed due to infection at the site, poor visualization of structures with the ultrasound, inability to obtain study drugs within a reasonable time frame, or unexpected operator difficulty in placing the block, the patient will not be included in the intention to treat analysis and dropped from the study.

4) Randomization:

- a) A computerized random number generator will be used by a staff of the Anesthesia Department not involved with the study. They will create a randomized numbered sequence with four groups (A, B, C or D) that will be given to the pharmacy team. This will be used to fill study syringes in the sequence according to the randomization schema.
- b) The UIHC Pharmacy will compound the study drugs and will fill and label the coded study syringes.
- c) Coded study syringes must be created and delivered within 30 minutes of the physician's request.
- d) The Pharmacy will keep a record of which patient received each coded syringe and the solution they contained.
- e) They will be given to the practitioner at the time of block placement.
- f) Practitioners will perform the block using the pharmacy coded study drug.

5) Masking:

- a) Masking will be accomplished by using coded labels on the study mixtures.
- b) At the end of the study enrollment, information given to the statistical analyst will be blindly coded as groups A, B, C or D for data analysis.
- c) The Pharmacy will keep the group codes until after data analysis is complete.
- d) The anesthesiologist and nurse assistants will be masked to the study mixtures.
- e) Any assisting anesthesia Staff, Fellows, Residents, CRNAs, SRNAs, or medical students will be masked to the study mixtures.

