- d)** Using sterile technique, cleaning the skin with tinted chlorhexidine and with the operators wearing caps, masks, and sterile gloves. The ultrasound probe will have a sterile sheath over it. Sterile ultrasound gel will be used.
- e)** With ultrasound guidance and nerve stimulator from 0.2 mA to 2.0 mA using a sterile Arrow 90mm insulated stimulation needle (StimuQuick).
- f)** If we are unable to stimulate the brachial plexus at the trunk level with the nerve stimulator, we will place local anesthetic in the region where the brachial plexus nerves are visualized using ultrasound based on the practitioner's experience with ultrasound-guided interscalene (brachial plexus trunks) nerve blocks.
- g)** Block start and end times will be recorded. Start time begins at block needle insertion. Stop time is the time of nerve block-needle withdrawal.
- h)** All patients will be monitored with blood pressure, pulse oximetry, ECG and have 2 liters per minute of oxygen administered by nasal cannula.
- i)** Emergency resuscitation equipment, intralipid, and emergency medications are present and immediately available for patient safety.

- j) Anesthesiologists will be present and/or immediately available should resuscitation efforts be necessary in the unlikely event of drug toxicity, cardiac arrest, or other adverse event.
- k) Any adverse outcomes (listed in “stopping rules” #23 below) will be reported to the Safety Monitors on the day it happens.
- l) The use of rescue blocks in the PACU will be counted and analyzed.

8) Statistics

- a) For our **primary outcome**, we will use ANOVA or Kruskall-Wallis test, after checking the normality of the data, to compare the duration of the analgesic block. If we find a difference among all 4 groups, we will use 2-sample t-test or Mann-Whitney U-test to explore differences between the individual groups.
- b) For our continuously distributed **secondary outcomes**, given that outcomes will be observed on every patient, we will use ANOVA or Kruskall-Wallis test. For outcomes with categories (nausea and vomiting and blood pressure), we will use the chi-square test. Similarly, we will explore the different group or groups using chi-square test or Fisher’s Exact test.
- c) We based our estimates upon Cumming’s, Candido’s and Casati’s previous studies and our clinical experience. We have estimated the expected additional analgesic time between the three groups.

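### No rule separates the study block from a PACU rescue block, so sensory and motor durations can include the second block and the primary duration may do so

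*Combined protocol and SAP*

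**What the plan says.** **Rescue blocks.** Under Techniques, item l: "The use of rescue blocks in the PACU will be counted and analyzed". No method follows, and rescue is not listed among the primary or secondary outcomes.

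**Who is analysed.** Under Consent, item c: "Patients with failed blocks will be included in the intention to treat analysis". Item d removes only patients whose block could not be placed; of those it says "the patient will not be included in the intention to treat analysis and dropped from the study". Rescue is not a listed reason for removal, and item b says consented patients are followed throughout.

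**Start of the clock.** Each duration starts at block-needle withdrawal. Techniques, item g, adds: "Stop time is the time of nerve block-needle withdrawal". Neither place says which needle counts if there are two blocks.

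**End of the clock.** Analgesic duration ends when the patient reports that "they first had awareness of painful sensation returning anywhere in the surgically operated upon area of the limb". Sensory duration ends when the patient reports that "they first had awareness of tactile (light touch) sensation returning anywhere in the blocked area". Motor duration ends at the patient-reported time of first biceps flexion. The times come from a form the patient fills in: "They will be telephoned within three days from the block to gather the data from the patient". If the form is lost or blank, the patient's memory is used.

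**Tests.** Statistics, items a and b, apply ANOVA or Kruskal-Wallis to the durations, with pairwise t-tests or Mann-Whitney tests for the primary outcome. There is no censoring and no rule for rescued patients. Item b assumes that secondary outcomes are observed on every patient.

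**The concern.** A rescue block is a second treatment given before the endpoint has been fully observed. Once it is in place, the end of the study block's sensory and motor effect can no longer be seen unless it came before the rescue. What the patient later writes down is the end of the second block, measured from the first needle.

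For pain the position is less clear-cut. A patient rescued for PACU pain has already had the event. But the only route by which that time reaches the analysis is the patient, recently operated on, writing it down or recalling it by telephone up to three days later. Such a patient could report when the rescue wore off, and the analyst would have no rule for replacing that time.

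At stake is the comparison between arms. Early failure of a study block is part of what the trial should measure. If rescued patients carry the second block's duration, a difference in failure between arms is diluted or masked.

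**Working it through.** **The plan's own figure.** Statistics, item d, gives 40 per group at 90% power and 0.05 type I error, but no SD, no control mean and no effect in hours, so it cannot be reproduced. Working backwards for two arms, two-sided: standardized difference = (1.960 + 1.282) × √(2/40) = 0.725. If the target is the 25% increase in the Hypothesis section, the implied coefficient of variation is 0.25/0.725 = 0.345. That supports an assumed CV of about 34% in the simulation below. The sample size itself is unaffected by this point.

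**Assumed inputs, none from the documents.** Working-block mean 12 h plain and 15 h adjuvant (ratio 1.25); pain after a failed block at 1.5 h; rescue effect lasting 12 h; rescue fraction p by arm as shown.

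**Formula.** Arm mean = (1 − p) × m + p × v. Here m is the working-block mean, and v is 1.5 h if PACU pain is reported or 1.5 + 12 = 13.5 h if the later time is reported. For example, the plain arm with p = 10% has mean 0.90 × 12 + 0.10 × 1.5 = 10.95 h, or 0.90 × 12 + 0.10 × 13.5 = 12.15 h.

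| Rescue, plain / adjuvant | v (h) | Plain mean (h) | Adjuvant mean (h) | Difference (h) | Ratio |
|---|---|---|---|---|---|
| 10% / 2% | 1.5 | 10.95 | 14.73 | 3.78 | 1.345 |
| 10% / 2% | 13.5 | 12.15 | 14.97 | 2.82 | 1.232 |
| 5% / 10% | 1.5 | 11.475 | 13.65 | 2.175 | 1.190 |
| 5% / 10% | 13.5 | 12.075 | 14.85 | 2.775 | 1.230 |
| 10% / 10% | 1.5 | 10.95 | 13.65 | 2.70 | 1.247 |
| 10% / 10% | 13.5 | 12.15 | 14.85 | 2.70 | 1.222 |
| 5% / 5% | 1.5 | 11.475 | 14.325 | 2.85 | 1.248 |
| 5% / 5% | 13.5 | 12.075 | 14.925 | 2.85 | 1.236 |

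**Direction.** Scoring through the rescue adds p × 12 h to each arm's mean. The difference between arms therefore changes by (p adjuvant − p plain) × 12 h: −0.96 h in the first pair and +0.60 h in the second. The arm with more rescue gains. With equal rates the difference is unchanged and the ratio drifts towards 1.

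**Size.** The ratio moves by 0.113 (10% / 2%), 0.040 (5% / 10%), 0.024 (10% / 10%) and 0.012 (5% / 5%).

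**Effect on the test.** In 3,000 simulated trials per scenario (40 per arm, log-normal durations, CV 34%, rescue duration mean 12 h and SD 2 h), Mann-Whitney rejects in about 89% with PACU pain scored versus 78% with the later time at 10% / 2%, and about 53% versus 80% at 5% / 10%.

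**Partial misreporting.** If only a quarter of rescued patients report the later time, the average v is 0.75 × 1.5 + 0.25 × 13.5 = 4.5 h. At 10% / 2% the means are 11.25 h and 14.79 h, ratio 1.315, a move of 0.03 rather than 0.11.

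**Sensory and motor durations.** For a rescued patient with no earlier return, the recorded value is the time to rescue plus the time the rescue lasts. Here the inclusion of the second block does not depend on misreporting: a patient who fills in the form correctly still produces it.

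**The case against.** The strongest objection is that the primary definition already deals with rescue. It asks for first awareness of pain, and the instruction to patients (Definitions, Duration of Analgesic Block, item iii) is to record when pain is first perceived in the surgical area, even on waking. A patient rescued for PACU pain has had that event. This stands. A reader might infer that every rescued patient's analgesic duration includes the second block; the documents do not say so. Nor can the word for pain coming back in item i be pressed, since the form itself is not in the documents and may not use it.

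Three other stronger readings also fail:

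- Sensory and motor times are not wrong for every rescued patient. A failed block is defined by cold sensation, so touch or biceps flexion may have returned before the rescue. The rescue block's site, drug and trigger are not stated either.
- No treatment effect is shown to reverse. The assumed cases keep the ratio at about 1.19 or above.
- Retention is stated only for failed blocks. For other rescued patients it is inferred from Consent, items b and d.

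The magnitude is also open to challenge. Every input is assumed, and the headline range takes all rescued patients as reporting the later time; with equal rates or partial misreporting the shift is small.

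What the objection does not remove is the sensory and motor problem, where no reading of the definitions recovers the study block's own end, or the absence of any rule to check or replace a late pain time.

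**Conclusion.** The concern holds in limited form. For sensory and motor durations, following the plan as written assigns the second block's duration to rescued patients without an earlier return. For the primary duration, the definition points to first pain, but its application rests wholly on patient reporting, so contamination is possible rather than established.

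The direction is not fixed; it depends on which arm has more rescue. The move of about 0.04 to 0.11 in the mean ratio requires unequal rescue of 2% to 10%, the assumed 12 h, 15 h, 1.5 h and 12 h values, and universal late reporting. At 10% / 2% the ratio crosses the 25% threshold (1.345 to 1.232); at 5% / 10% both values lie below it. These figures are illustrative. The documents give no rescue rate, so no actual bias can be quoted. The gap is worth closing because the remedy is cheap and must be chosen before group codes are broken.

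**What to change.** Add the following to the Statistics section before unmasking:

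- All durations start at withdrawal of the study-block needle.
- For a patient given a PACU rescue block, the analgesic end time is the earliest of the patient-reported first pain, the first pain recorded in PACU, and rescue needle insertion.
- For the same patients, sensory and motor end times are any return recorded before the rescue; otherwise, rescue needle insertion. Every patient then has a value and the planned rank tests still apply.
- A sensitivity analysis uses the times as reported, or a survival method with censoring at rescue. Censoring should not be the main approach: it is likely to be informative, since rescued patients tend to be those whose blocks worked worst, and ANOVA and Kruskal-Wallis cannot take censored times.
- Rescue counts are reported by arm beside the durations.

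The cost is a few lines of text and two times, first PACU pain and rescue needle insertion, taken from the PACU record. End times for rescued patients would then come partly from staff records. Ending a duration at rescue is also a convention: it can shorten a block that was still partly working, or record an analgesic end for a patient who reported no pain. The sensitivity analysis shows how much that matters. Nothing here alters when or how a rescue block is given.

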**A PROSPECTIVE TRIPLE-MASKED RANDOMIZED
CONTROLLED TRIAL MEASURING ANALGESIA
DURATION OF DEXAMETHASONE, BUPRENORPHINE, OR
CLONIDINE WITH ROPIVACAINE FOR INTERSCALENE
NERVE BLOCK**

STUDY PROTOCOL

- 1) Protocol Title:** A prospective triple-masked randomized controlled trial measuring duration of buprenorphine, dexamethasone, clonidine with ropivacaine for interscalene block
- 2) Protocol Version:** 2.0
- 3) Protocol Initiated:** June 18th, 2012
- 4) Protocol Revision Date:**
- 5) Protocol Completed Date:** *pending*
- 6) Principal Investigator:** [name]
- 7) Research Team:** [name]; [name], MS; [name], MPT; [name]; [name].; All research team members must be IRB certified.
- 8) Study Design:** This is a prospective randomized controlled triple-masked study looking at the duration of nerve block analgesia when using the listed adjuvants plus ropivacaine versus plain ropivacaine alone.
- 9) Questions:**
 - a)** When providing a interscalene nerve block (ISB) for painful shoulder surgery using the following four regimens:
 - i)** 0.75% plain ropivacaine. The reference comparator.
 - ii)** A mixture of 0.75% ropivacaine with 300 mcg buprenorphine
 - iii)** A mixture of 0.75% ropivacaine with 0.1 mcg/kg clonidine
 - iv)** A mixture of 0.75% ropivacaine with and 8mg dexamethasone
 - b)** Compared to 0.75% plain ropivacaine, will the adjuvant mixture:
 - i)** Increase block analgesic duration?
(Defined as elapsed times from block-needle withdrawal until patient-reported time that they were first aware of painful sensation in the operated region of the limb.)
- 10) Hypothesis:**

- a) **Null Hypothesis:** Compared to plain ropivacaine, the adjuvant mixture:
 - i) Will not increase the nerve block analgesic duration time by 25% or more.
- b) **Alternate Hypothesis:** Compared to plain ropivacaine, the adjuvant mixture:
 - i) Will increase the nerve block analgesic duration time by 25% or more.

11) Primary Outcome:

- a) Our primary outcome is the time from nerve block-needle withdrawal to return of:

- i) Painful perception in the operated upon area of the limb.

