- f) Patients will be masked to the study mixtures.
- g) Any person collecting and/or scribing the data will be masked to the study mixtures.
- h) Any person analyzing the data will be masked to the study mixtures.
- i) Once all the data has been collected and analyzed according to group code, the blinding on the study mixtures can be broken and the codes for the study mixtures made known.
- j) Safety monitors will not be masked to the mixtures. They can communicate with the pharmacy to unmask the mixtures for only themselves. They will not report the mixtures or pharmacy codes to anyone except for patient safety purposes.

k) The coded sample syringes will be kept for reanalysis in case there is any question of what mixture was given to any patient. The syringe contents can be tested by the pharmacy and a group code for that patient or set of patients will then be given to the analyst. The masking will remain intact.

6) Study Mixtures

a) The local anesthetic study mixtures volumes will be the same (32mL) and contained in two thirty-milliliter syringes with 16 mL in each. They consist of:

- i)** 0.75% Ropivacaine x 30mL (225 mg max dose) + 2 mL saline for a total volume of 32 mL
- ii)** 0.75% Ropivacaine x 30mL (225 mg max dose) with 300 mcg buprenorphine (1 mL) + 1 mL sterile saline for a total volume of 32 mL
- iii)** 0.75% Ropivacaine x 30mL (225 mg max dose) with 100 mcg/kg clonidine (0.1 mL) + 1.9 mL sterile saline for a total volume of 32 mL
- iv)** 0.75% Ropivacaine x 30mL (225 mg max dose) with 8mg dexamethasone (2 mL) + 0 mL sterile saline for a total volume of 32 mL.
- v)** *Note: If drug shortages occur during the study and we are unable to use the same concentration of any additive drugs (e.g. dexamethasone 10mg/mL instead of 4mg/mL), then a substitution will be allowed and the total volume in the syringe will be changed so that all syringes will be the same volume and final ropivacaine drug mass.*

7) Techniques:

All the blocks will be performed:

- a)** Either by, or under the direct supervision and direction of the Primary Investigator or regional anesthesia faculty listed on the investigation team.
- b)** In the Ambulatory Surgery Center at the University of Iowa Hospitals and Clinics using the posterior approach to the brachial plexus at the trunk level.
- c)** A timeout will be performed before the block to verify the patient, site of surgery and that we are blocking the correct side (already marked).

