- d) Using the above parameters, a sample size is 40 per group with 4 total groups calculates to a sum of 160 subjects while using 90% power and 0.05 type I error rate.

9) Safety Monitoring:

- a) An Anesthesiology Faculty member who is not involved in the study will act as safety monitor and will review the data and any complications when half of the patients (n = 80) have been completed.

10) Stopping Rules:

- a) Any incidence of patient complications that occur with an incidence higher than published data for the following complications for peripheral nerve blocks will be enough cause for the Safety Monitors to stop the study(31, 32). Numbers in parentheses below are the highest incidence reported in the referenced article for peripheral nerve block complications. The highest incidence of complications was reported to be from the supraclavicular block, which we will not be performing. We are relying on results reported from our own regional anesthesia follow-up clinic. This is a clinic developed here to see patients with troublesome complications of peripheral nerve blocks. The complication rates have been reviewed and studied since the clinic inception over 4 years ago(33). We are erring on the side of caution by using higher complication rates of the supraclavicular adverse event reports.
- b) Published Peripheral Nerve Block Complication rates:
 - i) Seizure (26.3/10,000)
 - ii) Cardiac arrest (Code Blue) (15.9/10,000)

- iii)** Respiratory Failure (15.9/10,000)
- iv)** Peripheral neuropathy (32/10,000)
- v)** Patient death (15.9/10,000)

References:

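### The pairwise tests after the four-group test are unadjusted: if exactly one adjuvant works, at least one of the two inert ones is called different from plain in 8–9% of trials

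*Combined protocol and SAP*

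**What the plan says.** The Questions section makes plain ropivacaine the reference arm and asks: "Compared to 0.75% plain ropivacaine, will the adjuvant mixture" increase block duration? That is three contrasts, one per adjuvant. The null hypothesis is worded in the same direction and with a margin: "Will not increase the nerve block analgesic duration time by 25% or more".

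For the primary outcome, Statistics a) states: "we will use ANOVA or Kruskall-Wallis test, after checking the normality of the data, to compare the duration of the analgesic block". It continues: "If we find a difference among all 4 groups, we will use 2-sample t-test or Mann-Whitney U-test to explore differences between the individual groups". No pairs are named, no sidedness is given, and no adjustment, ordering or hierarchy is stated there or elsewhere.

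The only error-rate statement is in the sample-size line, Statistics d): "160 subjects while using 90% power and 0.05 type I error rate". It does not say whether 0.05 applies to each test or to the set of three.

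Masking bears on the remedy. Masking c) says: "The Pharmacy will keep the group codes until after data analysis is complete". Masking h) says: "Any person analyzing the data will be masked to the study mixtures".

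**The concern.** A significant four-group test says that some difference exists. It does not say which adjuvant differs from plain, so the follow-up tests carry the trial's conclusions.

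With four groups, an omnibus gate followed by unadjusted tests protects the error rate only when all four arms are equal. If one adjuvant works, it opens the gate by itself. The two inert adjuvants are then each tested against plain at 0.05, with nothing holding the pair at 0.05. At stake is a report that an adjuvant changes block duration when it does not.

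**Working it through.** **Inputs.** From the documents: 40 per arm, four arms, 0.05, 90% power, omnibus test and then pairwise tests. Assumed: normal data with equal SD, two-sided tests, and effects in SD units, because the documents give no SD and no numerical effect.

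**The plan's own figure.** 4 × 40 = 160 agrees. The 40 per arm cannot be derived forward without an effect and an SD. Solving backwards for one unadjusted two-sided comparison gives d = (1.960 + 1.282) × √(2/40) = 0.725 SD, or 0.734 SD with the exact t distribution. I use 0.734 SD as a reference effect. It is not a figure from the plan.

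**Rough bound.** Once the gate is open, two independent null tests at 0.05 would give 1 − 0.95² = 9.75%. The two contrasts share the plain arm, so they are correlated and the true value is somewhat lower.

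**Simulation of the plan.** ANOVA gate (F with 3 and 156 df), then unadjusted t-tests (78 df), 200,000 trials per scenario. The error counted is at least one inert adjuvant called different from plain, in either direction.

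| True state | Error against plain |
|---|---|
| None works | 4.0% |
| One works, 0.25 SD | 5.1–5.2% |
| One works, 0.5 SD | 8.2–8.3% |
| One works, 0.734 SD | 9.0–9.1% |
| One works, 1 to 2 SD | 9.0–9.1% |
| Two work | about 5% |
| Three work | no null contrast with plain |

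Ranges show repeat runs. The Monte Carlo standard error at 9% is √(0.09 × 0.91/200,000) = 0.06 percentage points.

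The Kruskal-Wallis and Mann-Whitney branch gives much the same: 7.7–8.0% at 0.5 SD and 8.8–9.0% from 0.725 to 1 SD. Choosing the branch by a normality check was not simulated.

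**Two narrower error rates**, with one adjuvant working at 0.5 SD or more (runs agree to about 0.1 point):
- One named inert adjuvant called different from plain: about 4.6–5.0%.
- At least one inert adjuvant falsely called longer than plain: about 4.0–4.5%.

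**Closed test.** An adjuvant is called different from plain only if the four-group test, both three-group tests containing plain and that adjuvant, and the pairwise test are all significant at 0.05. Every combination of true nulls then has its own 0.05 test, so the chance of any false difference from plain is held at 0.05. Simulated with one adjuvant working at 0.5 to 1.5 SD, the error is 4.0–4.2%.

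**Power at an assumed 0.734 SD, 40 per arm.**

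| | Plan | Closed | Gated step-down | Holm | Dunnett |
|---|---|---|---|---|---|
| One works: detect it | 87% | 86% | 83% | 80% | 82% |
| Two work: detect both | 83% | 80% | 74% | 74% | 72% |
| Three work: detect all | 78% | 77% | 77% | 77% | 64% |

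The gated step-down tests the ordered p-values at 0.025, 0.025 and 0.05. Once the four arms are known not to be all equal, at most two contrasts with plain can be null, and 0.05/2 = 0.025.

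**The case against.** **The plan says these tests explore.** That would answer the point if another test compared each adjuvant with plain. None does.

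**Three different drugs are three separate questions.** Whether such contrasts need familywise control is debatable, and the plan does not say that its 0.05 is familywise. This stands as a reason for modest weight. However, the plan already gates the set with one omnibus test, so completing that gate follows its own logic.

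**The case is narrow.** This stands. The inflation needs exactly one effective adjuvant and at least a moderate effect. The Study Background Information section reports prolongation in earlier studies of all three. If all three work, no contrast with plain can be falsely positive, and an adjustment only costs power.

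**The hypothesis is directional.** Under two-sided tests, a false claim of longer duration stays below 0.05. This also stands. It is nearly twice the 2.5% that a two-sided familywise 0.05 would allow in that direction, but the documents do not set that benchmark.

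A reader might infer three stronger things that the documents do not support:
- That any given inert adjuvant has nearly double the nominal error. It does not; its rate is at most about 5%. The 8–9% is for at least one of two.
- That false claims of longer duration run at about 9%. That requires one-sided tests at 0.05, and the plan states no sidedness.
- That 11–12% is the relevant error. That figure adds adjuvant-versus-adjuvant pairs, which the Questions section does not ask about.

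**Conclusion.** The point holds as a cheap improvement, not as a serious flaw. With exactly one effective adjuvant at about 0.5 SD or more, the chance of at least one false difference from plain is 8–9% instead of 5%. In every other configuration it is about 5% or less.

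The size rests on 40 per arm, normal data with equal SD, two-sided 0.05 tests and assumed effects in SD units. The null examined is zero difference. It is not the hypothesis section's null of an increase below 25%, so 8–9% is not the error rate of that hypothesis. The margin is a separate issue.

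**What to change.** In Statistics a):

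1. Name the three adjuvant-versus-plain contrasts as primary, two-sided, at a familywise 0.05.
2. Keep the four-group gate and complete it as the closed test described above, with ANOVA and t-tests or with Kruskal-Wallis and Mann-Whitney tests. Holm or the gated step-down is acceptable. Dunnett also controls the error but costs more when several adjuvants work.
3. Label adjuvant-versus-adjuvant tests exploratory.
4. To keep masking, compute the results with each code A to D as candidate control, and read only the set for plain once the codes are broken. In all this needs one four-group, four three-group and six pairwise tests. It adds no multiplicity, because the code alone fixes which set is read.

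**Cost.** A few sentences, and no extra patients if a small loss of power is accepted. At an assumed 0.734 SD, the closed test costs about 1 to 3 percentage points across the three rows of the power table. To recover 90% power at an assumed 0.725 SD with one adjuvant working takes about 46 per arm, against about 44 for the plan's own gated procedure. The change controls the error against zero difference only and does not test the 25% margin.
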